### **11.3 Treatments (study drug, rescue medication, other concomitant therapies, compliance)**

Data for total dose of infusion, infusion rate and total time of infusion will be listed by treatment group and subject.

Data for concomitant therapies will be listed by treatment group and subject.

### **11.4 Analysis of the primary variable(s)**

The primary analyses for this study will characterize the safety of 18 hour infusion of CLR325 in patients with stableheart failure.

#### **11.4.1 Variable(s)**

The primary variable will be the occurrence of adverse events in patients in the study.

#### **11.4.2 Statistical model, hypothesis, and method of analysis**

All information obtained on adverse events will be displayed by treatment and subject.

The number and percentage of subjects with adverse events will be tabulated by body system and preferred term with a breakdown by treatment. A subject with multiple adverse events within a body system is only counted once towards the total of this body system.

The occurrence of adverse events will be examined by treatment. Both the total number of adverse events, and the preferred term for the adverse event will be compared by treatment group.

It is hypothesized that the estimated rate of serious adverse events in the treated group equal to that in the placebo group. The estimated probability of serious adverse events will be examined with 90% confidence limits around the estimated probability. Summary tables with the number, percentage, and severity of adverse events will be provided to assess safety and tolerability per treatment groups. The number and percentage of patients with adverse events will be tabulated by body system and preferred term with a breakdown by treatment group. The difference in the occurrence of adverse effects will be quantified by using the Fisher's Exact Test. Separate tables and listings will be presented indicating event severity and study drug relationship. All safety laboratory and other continuous data will be listed, and descriptive statistics will be generated.

All data for vital signs, cardiac monitoring, ECG evaluations, hematology, blood chemistry and urinalysis will be listed for each subject and summarized by descriptive statistics per treatment and for time interval where appropriate. For all these safety variables, if ranges are available, abnormalities will be flagged. The individual data and descriptive statistics will be also shown as graphical outputs. Cardiac monitoring data will be listed and descriptive statistics generated by treatment and time. Graphical presentations will be generated to show the individual time course of the data, including concentration-response plots.

Pharmacokinetic results will be summarized by descriptive statistics per treatment.

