## Protocol synopsis

Protocol number	CLR325X2202
Title	A randomized, subject and investigator-blinded, placebo-controlled study of CLR325 in chronic stable heart failure patients
Brief title	Safety, pharmacokinetics and efficacy study of CLR325 in stable heart failure patients.
Sponsor and Clinical Phase	Novartis Phase IIa
Intervention type	Drug
Study type	Interventional
Purpose and rationale	The purpose of this study is to determine the safety and tolerability of CLR325 in heart failure patients to determine if further clinical development of the drug in this indication is warranted.
Primary Objective(s)	To determine the safety and tolerability of an 18-hour i.v. infusion of CLR325 in stable heart failure patients
Secondary Objectives	To determine the pharmacokinetics and immunogenicity of CLR325, and the active metabolite, CQJ295, during an 18-hour infusion of CLR325 in heart failure patients.
Study design	
This is a non-confirmatory, randomized, subject and investigator-blind, placebo-controlled study of an 18-hour infusion of CLR325 in stable heart failure patients (who have a clinically indicated pulmonary artery catheter in place) to assess safety, tolerability, and pharmacokinetics in this patient population. This study has an adaptive dose design. A maximum of 40 patients will be randomized. Initially, one cohort will be dosed: 6 patients with CLR325 and 2 with placebo.
 
Corporate Confidential Information

Population	Patients with stable heart failure >18 years of age
Inclusion criteria	
Written informed consent must be obtained before any assessment is performed.
 
Able to communicate well with the investigator, to understand and comply with the requirements of the study.
 
Male and female patients >18 years of age.
 
Patients must weigh between 50 kg and 140 kg to participate in the study.
 
Patients with a cardiac ejection fraction of <math>\leq 45\%</math> as assessed within the last 6 months.
 
In the opinion of the investigator, heart failure patients who will not require a change in their dose of ACE, ARB, <math>\beta</math>-blocker, mineralocorticoid receptor antagonist, or diuretic for 24 hours after randomization.
 
For PA catheter cohorts, patients who are planned to have a clinically indicated pulmonary artery catheter in place prior to randomization.

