## **Corporate Confidential Information**

### **3 Investigational plan**

#### **3.1 Study design**

This is a non-confirmatory, randomized, subject and investigator-blind, placebo-controlled study of an 18-hour infusion of CLR325 in stable heart failure patients (who may have a clinically indicated pulmonary artery catheter in place) to assess safety, tolerability, and pharmacokinetics in this patient population. Initially, one PA catheter cohort will be dosed: 6 patients with CLR325 and 2 with placebo randomized using a block randomization scheme. The first cohort of patients will be those with chronic stable heart failure. For subsequent cohorts, patients with acute decompensation who have been stabilized following hospital admission may also be enrolled. Following completion of the first cohort, subsequent cohorts may enroll concurrently as determined by the sponsor.

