## **Corporate Confidential Information**

The study will be comprised of a screening period of approximately 7 weeks (Day -45 to Day 1), a baseline period (Day 1), a treatment period (Day 1-2) and a follow up period (Days 3-28). Each treatment period will be comprised of a baseline pre-dosing interval (hour -1 to hour 0), an inpatient dosing interval (hour 1 to hour 18), and an inpatient post-dosing interval (hour 18 to hour 28). In addition, patients will have a follow-up visit (Day 10) and an end-of-study visit on Day 28.

On Day -45 to 1, screening evaluations will be performed. Study inclusion/exclusion criteria as well as medication use will be assessed during the screening and baseline periods. Patients who meet all of the inclusion and none of the exclusion criteria at screening will report to the study site on Day 1 of the baseline period, at a time specified by the investigator, and if they continue to meet all inclusion and none of the exclusion criteria, will remain in-house until the final 28 hour inpatient assessment in the treatment period.

[figure not shown]
On Day 1, pre-dose laboratory evaluations, cardiac hemodynamic monitoring, and 3-lead continuous telemetry monitoring will be performed. The sponsor will pre-specify if hemodynamics are to be monitored by a PA catheter, echocardiography, or both for each cohort. For PA catheter cohorts, cardiac hemodynamics will be monitored continuously using a pulmonary artery catheter (that will have been placed for standard of care clinical indications by the subject's caregiver prior to randomization in the study)

**Corporate Confidential Information** Intracardiac pressures (right atrial, pulmonary artery) will be recorded every hour during the treatment period. Cardiac outputs will be obtained at hours -1, 0, 1, 3, 6, 8, 10, 12, 18, 20, 24, and 28 of the treatment period. If not needed for standard of care clinical indications, the pulmonary artery catheter may be removed after the final cardiac output measurement at hour 28. For echocardiographic cohorts, echocardiograms will be obtained during the treatment period as specified in the SOM. Note that the sponsor's decision regarding obtaining the echocardiogram will be applied uniformly across all patients in the cohort.

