### **6.2 Treatment arms**

Patients will be assigned to one of the following 2 treatment arms in fixed randomization ratio (CLR325:Placebo):

- Single dose of CLR 325 (i.v.)
- Single dose of Placebo (i.v.)

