### **11.6 Sample size calculation**

The sample size is based on clinical considerations for safety review of this study. With 6 active subjects in a dose cohort, there is a 74% chance of at least one subject having a particular adverse event when the event rate is 20%. With 4 active subjects in a dose cohort, this chance is 60%.

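### The CLR325-placebo adverse-event test takes no account of cohort or dose; stratifying it by cohort costs almost nothing and can recover power

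*Protocol*

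**What the plan says.** Section 6.2 of the protocol defines two arms: "Patients will be assigned to one of the following 2 treatment arms in fixed randomization ratio". It does not give the ratio. Section 11.4.2 sets the serious-adverse-event hypothesis as one treated group against one placebo group. On adverse events in general it says "The number and percentage of patients with adverse events will be tabulated by body system and preferred term with a breakdown by treatment group", and it names Fisher's exact test for the difference. No stratification factor is given, and Section 11.4.4 foresees no supportive analysis.

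The design is built from cohorts that need not be alike:

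- **Dose.** The synopsis says "This study has an adaptive dose design", and Section 6.1.1 has the pharmacist prepare a cohort-dependent dose.
- **Patient type.** Cohort 1 is chronic stable heart failure. Section 3.1 then says "For subsequent cohorts, patients with acute decompensation who have been stabilized following hospital admission may also be enrolled".
- **Monitoring.** Section 3.1 also says "The sponsor will pre-specify if hemodynamics are to be monitored by a PA catheter, echocardiography, or both for each cohort".
- **Eligibility.** Exclusion 15 in Section 4.2 (recent admission for decompensation) applies only to echocardiography cohorts.

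On allocation, Section 3.1 describes the first cohort as "6 patients with CLR325 and 2 with placebo randomized using a block randomization scheme". Section 11.6 also considers a smaller cohort: "With 4 active subjects in a dose cohort, this chance is 60" per cent.

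**The concern.** Cohort is the unit within which patients are enrolled and, visibly for cohort 1, randomized. It is also likely to predict adverse events. Section 3.6.5 gives complication rates for the pulmonary artery catheter, and a patient recently stabilized after decompensation may not have the same background risk as a chronic stable one. A test that ignores such a factor is usually less sensitive than one that conditions on it. If the allocation ratio also changes between cohorts, the two arms contain different mixes of cohorts and the crude difference is no longer a clean treatment contrast.

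Dose raises a second question, because the protocol does not say whether a treatment group means all CLR325 patients or each dose level. Pooling all doses dilutes an effect confined to some of them. Setting one dose against all placebo patients compares one cohort with a mixture of cohorts. The study is meant to inform whether development should continue, so a weak or blurred safety comparison matters even though the trial is non-confirmatory.

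**Working it through.** **The plan's own figures (Section 11.6).** The chance of at least one event at a 20% rate is 1 − 0.8^n. For n = 6 it is 1 − 0.262 = 73.8% (stated 74%). For n = 4 it is 1 − 0.410 = 59.0% (stated 60%). Both reproduce to within a point.

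**Inputs from the protocol.** At most 40 patients; cohort 1 is 6:2; a cohort with 4 active patients is considered; Fisher's exact test. **Assumptions.** Background rates, the odds ratio, a two-sided 0.05 level (the protocol states none for this test), and 1 or 2 placebo patients beside 4 active.

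**1. Allocation ratio.** 6:2 is 3:1. Four active patients at 3:1 would need 4/3 = 1.33 placebo patients. A full cohort planned with exactly 4 active patients would therefore depart from the first cohort's ratio.

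**2. Bias in the pooled contrast with no drug effect.** For two cohort types, bias = (share of the second type among active − share among placebo) × (background difference).

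- Constant ratio: the shares are equal, so the bias is 0.
- Two 6:2 and three 4:1 cohorts (24 active, 7 placebo): 12/24 − 3/7 = 50.0% − 42.9% = +7.1 points. A 20-point background difference gives 0.071 × 20 = +1.4 points.
- Two 6:2 and three 4:2 cohorts (24 active, 10 placebo): 12/24 − 6/10 = −10 points. A 20-point difference gives −2.0 points.

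These are the largest imbalances over all mixes of the two cohort types within 40 patients. For scale, the upper catheter-complication rates in Section 3.6.5 sum to 4 + 1.9 + 3 + 1 = 9.9 points, which would mean a bias of about 1 point or less.

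**3. Type I error of the pooled Fisher test**, by exact enumeration with backgrounds of 10% and 50% and no drug effect: 0.024 for two 6:2 and four 4:2 cohorts (28 v 12), and 0.013 for three 6:2 and three 4:1 cohorts (30 v 9). Both are below the nominal 0.05.

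**4. Power, pooled Fisher against an exact conditional test stratified by cohort.** The active rate is 6q/(1 − q) ÷ [1 + 6q/(1 − q)] for background q. For q = 10%, 20%, 30%, 40%, 50% this gives 40%, 60%, 72%, 80%, 86%. Results are simulated. At 0.05 they are given as ranges where repeated runs differed, and the 0.10 column is from one set of 3,000 runs.

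| Scenario | Two-sided 0.05: pooled v stratified | Two-sided 0.10: pooled v stratified |
|---|---|---|
| Five 6:2, background 20% throughout | 50–51% v 52–53% | 68% v 68% |
| Five 6:2, backgrounds 10–50% | 42–43% v 50–52% | 58% v 62% |
| Two 6:2 at 10%, four 4:2 at 50% | 31–33% v 49–50% | 52% v 64% |

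With no drug effect in the third scenario, the stratified test rejects in 3.3% of trials at nominal 0.05, so its gain does not come from excess false positives.

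**5. Dose.** With five 6:2 cohorts (30 v 10), placebo at 20% and affected doses at 60%, pooled Fisher power at 0.05 is 50% if all five doses act, 19% if three do, 9% if two do and 3.7% if one does. One dose of 6 against all 10 placebo patients has 32%. One dose of 6 against its own 2 placebo patients has 3%. The smallest p-value attainable inside a cohort is 1/28 = 0.036 (6:2), 1/15 = 0.067 (4:2) or 1/5 = 0.20 (4:1).

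**6. One dose against placebo pooled over cohorts.** With five 6:2 cohorts, 8 of the 10 placebo patients come from other cohorts. If the dose's cohort has background b and the others average c, the crude difference under no effect is b − (0.2b + 0.8c) = 0.8(b − c). A 10-point background difference gives 8 points.

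**The case against.** Much can be said for leaving the plan alone. The trial is non-confirmatory, is sized on clinical grounds and claims no power for this comparison, so no stated operating characteristic is broken. With a constant ratio, Fisher's test on the pooled arms is valid. The protocol does not define a treatment group as all doses pooled. Pharmacokinetics are summarized per treatment, and Section 11.6 reasons per dose cohort, so dose level is a possible reading. Adverse events are listed by subject, and so are dose and infusion rate (Section 11.3), so the dose at which an event occurred can be recovered. Sections on later cohorts are blacked out, and an analysis plan that is not at hand may add detail.

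Most of this stands, and it limits the point. A reader might infer more, and the documents do not support it:

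- *That the primary contrast is confounded by cohort.* This needs a varying ratio, and the bias is then small.
- *That false positives are inflated.* The pooled test stays below its nominal level in the mixed 6:2 with 4:1 or 4:2 cases. Serious inflation needs allocations and background gaps that appear nowhere in the protocol.
- *That cohorts cannot share one ratio.* The placebo number beside 4 active patients is not visible, and the protocol does not say that 4 active is a planned full cohort.

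What does not stand is the appeal to later detail. The protocol itself names the arms, the contrast and an unstratified test, so the point concerns a stated choice rather than a missing one.

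**Conclusion.** The point holds as an improvement worth making, not as a flaw that invalidates the trial. The stated test discards cohort, a factor the design makes potentially prognostic. The cost is about 9 points of power (43% v 52%) when backgrounds run from 10% to 50% over five 6:2 cohorts, more in a mixed-ratio case, and nothing when backgrounds are equal. Any bias in the pooled contrast is zero at a constant ratio and about 2 points or less per 20-point background difference otherwise. The larger hazard is an unadjusted comparison of one dose with placebo from all cohorts, which carries 0.8 times the background difference with five 6:2 cohorts. The power figures rest on an assumed odds ratio of 6, assumed background rates and an assumed two-sided 0.05 level. At 0.10 the gain is smaller (58% v 62% in the same case). The bias figures rest on assumed placebo numbers for the smaller cohort.

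**What to change.** 1. In Section 11.4.2, replace the unstratified Fisher test for the overall CLR325-placebo contrast with an exact test stratified by cohort, and report a Mantel-Haenszel risk difference.
2. Define treatment group, and tabulate adverse events by CLR325 dose level and cohort as well as pooled. Keep each dose against its own cohort's placebo descriptive, since 6 against 2 has almost no power. Any display of one dose against all placebo patients should say that it mixes cohorts.
3. In Section 6.2, state the allocation ratio for each cohort size, so that the single fixed ratio is reconciled with the 6:2 first cohort and the 4-active cohort of Section 11.6.

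The cost is a few sentences and a little programming, with no added patients. The downside is that cohort-level tables will be sparse.

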## 2 Study objectives

### 2.1 Primary objective(s)

Primary objective(s)	Endpoints related to primary objective(s)

To determine the safety and tolerability of an 18-hour i.v. infusion of CLR325 in stable heart failure patients.

	

Frequency of adverse events in CLR325 treated patients as compared to patients treated with placebo.

Frequency of clinically significant changes in hematology or clinical chemistry laboratories or changes in blood pressure or heart rate.

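### Section 11.4.2 assigns Fisher's exact test to measure the adverse-event difference, which it cannot do, and puts its only interval and written hypothesis on serious events

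*Protocol*

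**What the plan says.** Section 11.4 gives the aim as description: "The primary analyses for this study will characterize the safety of 18 hour infusion of CLR325". Section 11.4.1 names the variable: "The primary variable will be the occurrence of adverse events in patients in the study". The first primary endpoint in Section 2.1 is comparative: "Frequency of adverse events in CLR325 treated patients as compared to patients treated with placebo".

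Section 11.4.2 then makes three separate statements:

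- Hypothesis: "It is hypothesized that the estimated rate of serious adverse events in the treated group equal to that in the placebo group".
- Interval: "The estimated probability of serious adverse events will be examined with 90% confidence limits around the estimated probability".
- Between-group difference: "The difference in the occurrence of adverse effects will be quantified by using the Fisher's Exact Test".

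The same section plans numbers and percentages of patients with AEs by treatment, body system and preferred term, and separate tables by severity and relationship. Section 11.5.2 repeats the tabulation and adds no estimate of a difference. Section 11.4.4 says supportive analyses do not apply.

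**The concern.** The sentence on the AE difference names a method that does not deliver what the sentence asks of it. A small p-value can come from a large difference in few patients or a moderate one in many. A p-value of 1 can sit beside a sizeable observed difference when the groups are small.

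The interval does not fill the gap. It covers SAEs rather than all AEs, and it surrounds one probability rather than a contrast between arms. Percentages by arm are tabulated, so a reader can subtract to get the observed AE difference. The uncertainty of that difference is not available from anything named in the section.

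Section 1.2 says the study is to help decide whether further development is warranted. For that, the useful question is how large an AE excess over placebo the data still allow. The stated method does not answer it.

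**Working it through.** **Inputs.** First cohort: "Initially, one PA catheter cohort will be dosed: 6 patients with CLR325 and 2 with placebo randomized using a block randomization scheme" (Section 3.1). Ceiling: "A maximum of 40 patients will be randomized" (synopsis). Interval level: 90% (Section 11.4.2). Assumed, not stated: the 6:2 ratio held throughout, giving 40 × 6/8 = 30 active and 10 placebo; Clopper-Pearson for the single-rate limits; all event counts below.

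**The plan's own figures.** The protocol gives no number for the AE comparison. Its only related figures are in Section 11.6, the chance of seeing at least one event at a 20% rate: 1 - 0.8^6 = 73.8% (stated 74%) and 1 - 0.8^4 = 59.0% (stated 60%). These concern detecting an event in the active arm and say nothing about a difference from placebo.

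**Step 1: Fisher's p at 6 v 2.** With x active and y placebo events, the table probability given the total is C(6,x)·C(2,y)/C(8,x+y). The two-sided p sums all tables with the same total that are no more probable than the one observed.

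- 6/6 v 0/2, and its mirror 0/6 v 2/2: p = 1/28 = 0.036. These are the only two tables below 0.05, and also the only two below 0.10.
- 5/6 v 0/2: p = 6/56 = 0.107, the next smallest value.
- 2/6 v 0/2 (+33 points): its probability 15/28 is the largest for that total, so p = (15 + 12 + 1)/28 = 1.0.
- 4/6 v 2/2 (-33 points): likewise p = 1.0.

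Over all 7 × 3 = 21 tables, 9 give p = 1.0. Their observed differences run from -33 to +33 points.

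**Step 2: the p-value does not track size.**

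| Active | Placebo | Difference (points) | Fisher p |
|---|---|---|---|
| 5/6 | 0/2 | +83 | 0.107 |
| 24/30 | 5/10 | +30 | 0.103 |
| 3/6 | 0/2 | +50 | 0.464 |
| 15/30 | 0/10 | +50 | 0.006 |

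The first pair has nearly the same p and very different differences. The second pair has the same difference and very different p.

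**Step 3: what an interval adds.** Take 3/30 v 1/10: difference 0, p = 1.0.

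- Wilson 90% limits (z = 1.645): 0.041 to 0.226 active, 0.023 to 0.348 placebo.
- Newcombe lower limit: 0 - √[(0.100 - 0.041)² + (0.348 - 0.100)²] = -0.255.
- Newcombe upper limit: 0 + √[(0.226 - 0.100)² + (0.100 - 0.023)²] = +0.147.
- Miettinen-Nurminen limits for the same data: -0.262 to +0.156.

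The data would still allow an excess of about 15 points, which p = 1.0 does not show. If these events were SAEs, the planned single-rate limits would be 3% to 24% on active and 1% to 39% on placebo. Neither bounds the difference.

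**Step 4: choice of interval.** Exact coverage of nominal 90% intervals, over true rates of 5% to 95% in each arm in 5-point steps:

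| Design | Method | Minimum | Mean |
|---|---|---|---|
| 6 v 2 | Miettinen-Nurminen | 85% | 93% |
| 6 v 2 | Newcombe | 81% | 91% |
| 30 v 10 | Miettinen-Nurminen | 88% | 91% |
| 30 v 10 | Newcombe | 88% | 90% |

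Miettinen-Nurminen holds its level better in the smallest cohort, and the two are close at 30 v 10.

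**The case against.** The strongest reply is that the fault is one loose verb. Had the sentence said the difference would be tested, nothing in it would be wrong, and the tables already show the observed rates by arm. The effect measure and its interval could be left to an analysis plan that is not at hand. Equality is the ordinary null of Fisher's test, so AEs carry an implied hypothesis, and extra attention to SAEs, a subset of AEs, is reasonable. The study is non-confirmatory, its size was not set by power, and the pausing criteria in Section 7.4 do not use the test. Finally, intervals from a 6 v 2 cohort say little: over the 21 tables the 90% Miettinen-Nurminen interval has a median width of about 100 points (range 61 to 110).

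Much of this is right, and it limits the weight of the point. No wrong claim of equal safety is built into the plan, and no stated decision changes. But the objection is to what the protocol states, not to what it leaves out. An analysis plan faithful to Section 11.4.2 would produce p-values as the measure of the primary comparison. Changing the verb alone would leave the primary endpoint with no stated measure of the difference or its precision. Wide intervals are an honest account of what 2 placebo patients can show; a p-value of 1.0 from the same data hides it. The 30:10 figures rest on an assumed split and are illustrations, but the 6 v 2 results use only the stated cohort.

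**Conclusion.** The point holds. Section 11.4.2 names a method for the primary comparison that does not measure the difference, and its only interval and only written hypothesis address SAEs rather than the declared primary variable. In the stated first cohort, p = 1.0 covers observed differences across a 66-point span, and no table short of complete separation of the arms falls below 0.10. The illustration at 40 patients depends on a 30:10 split; cohorts may differ, since Section 11.6 also mentions 4 active patients per cohort and the adaptive dosing detail is blacked out. The change should be made, but its benefit is clearer reporting, not rescue of a failed analysis.

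**What to change.** In Section 11.4.2, replace the Fisher sentence with wording such as: *The proportions of subjects with at least one AE and with at least one SAE will be compared by the risk difference (CLR325 minus placebo) with a two-sided 90% Miettinen-Nurminen score confidence interval. Any Fisher's exact p-value is descriptive.* Add whether the contrast is made by dose or with doses pooled, because the design allows more than one dose.

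Reword the SAE hypothesis as estimation: *The SAE rate in each group and the difference between groups will be estimated.*

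A minor addition: the synopsis and Section 11.4.2 compare total numbers of AEs by group. Allocation is unequal, so show these per patient as well.

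The cost is protocol wording and a little programming, with no change to data collection or sample size. The intervals will be visibly wide, and with 2 placebo patients their coverage is only approximate.
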